
6. STUDY PROCEDURES

6.1 Screening Procedures

All applicants will be screened by phone to determine whether they potentially meet eligibility criteria. We will obtain a waiver of written documentation of consent for the telephone screen. Those who remain interested in the trial will be scheduled for an in-person interview. The Weight and Lifestyle Inventory (WALI), an assessment of general eating and lifestyle behaviors, the Weight Bias Internalization Scale (WBIS), and the Beck Depression Inventory (BDI) will be mailed or emailed to eligible participants following the phone screen and completed by them prior to their screening/informed consent visit. The in-person interview will be conducted by a psychologist, who will obtain informed consent and evaluate participants' behavioral eligibility (i.e., willingness and appropriateness to participate). This will include our assessment of the applicant's mood (as measured by interview and the BDI) and suicidality (including history of suicidal ideation and behavior). Applicants who report active suicidal intent will be escorted to the emergency room at the Hospital of the University of Pennsylvania. (If applicants report suicidal intent while being screened by phone, they will be instructed to report to their nearest emergency room and/or to call the suicide hotline, for which the phone number will be provided

during the call. If applicants reporting suicidal intent by phone refuse to seek immediate help, a wellness check may be requested from the local police department.)

Applicants who remain interested and pass the behavioral assessment will proceed to provide a medical history, which will be reviewed by the study physician or nurse practitioner to determine medical eligibility. Medical eligibility will be confirmed with blood test results. Applicants with a history of cardiac events or other significant CVD risk factors may also be asked to provide written verification from their primary care physician stating that they are healthy enough to participate in a weight loss program.

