BWL intervention. Participants in this group will be provided with 20 weekly BWL sessions, based on the Diabetes Prevention Program (DPP) manual,⁵⁹ followed by 6 monthly weight loss maintenance sessions and 3 every-other-month sessions (for a total of 29 visits over 72 weeks). A diet of 1200-1499 calories per day will be prescribed for participants < 250 lb, and 1500-1800 for those ≥ 250 lb.^{59,60} Participants will be instructed to eat a balanced deficit diet with approximately 15-20% of kcal from protein, 20-35% from fat (less than 10% from saturated fat), and the remainder from carbohydrates.⁵⁹ Session topics during the first 20 weeks will include self-monitoring, stimulus control, slowing eating, social support, cognitive restructuring, portion sizes, and goal-setting.⁵⁹ Those during weeks 21-72 will focus on continued self-monitoring and skills required for weight loss maintenance and relapse prevention. BWL sessions will last 90 minutes. Beginning at week 5, 60 minutes of the group session will be devoted to BWL content, with an additional 30 minutes devoted to discussing recipes and food preparation.

Physical activity will be prescribed at a level consistent with data showing that ≥ 250 min/wk is associated with improved long-term weight loss.^{12-14,61} Activity will begin at week 2 with 60 min/wk, and will gradually progress by 10 minutes over 2-4 week intervals until achieving 150 min/wk by week 20, 200 min/wk by week 46, and 250 min/wk by week 72. Participants will be instructed to spread the 150-250 minute doses of activity equally across at least 5 days, and to accumulate their structured physical activity in bouts that are ≥ 10 minutes in duration. Moderate intensity will be prescribed with an emphasis on walking; the vast majority of our research participants self-select this form of activity.

Participants who cannot attend any given group session will be offered a brief (10-20 minute) make-up session (in person or by phone) during the week with the group leader or a study staff member. Participants may also meet briefly with the group leader individually, outside of group sessions, up to 3 times during the initial 20-week study period if they have not lost at least 1% of their body weight by week 4, report difficulty controlling their eating, or describe other challenges preventing them from adhering to the program that cannot be fully covered during group sessions.

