Stigma + BWL intervention. Participants in this group will receive the same BWL program described above, which will be combined with a stigma-reduction intervention. Beginning at week 5, the 60-minute BWL sessions will be followed by 30 minutes devoted to stigma-related content. Session topics will be based on those tested in a previous pilot study, including: psychoeducation about weight and weight stigma; challenging myths and cognitive distortions related to weight; strategies for coping with instances of stigma; and increasing empowerment and body esteem. The effects of weight stigma on health behaviors will be discussed, and sessions will focus specifically on helping participants overcome stigma-related barriers to physical activity. For example, they will be given strategies to cope with anticipated stigma while exercising in public spaces (e.g., while walking), as well as to challenge self-critical beliefs (e.g., that they are lazy) which may otherwise lead them to avoid exercising. These concrete strategies, along with reducing WBI and improving self-confidence, are intended to increase participants' self-efficacy for and engagement in physical activity. In the monthly and every-other-month weight loss maintenance sessions from weeks 21-72, strategies for coping with weight stigma and challenging internalized beliefs will be reviewed, and participants will be encouraged to use these strategies specifically with physical activity.

As with the BWL Intervention, participants who cannot attend group sessions or are experiencing difficulties adhering to the program will be eligible for brief individual meetings with the group leader or study staff (as described above).

Adjustments to treatment sessions due to COVID-19. During the pandemic, all group sessions will be conducted virtually on the platform BlueJeans. Group members who do not have access to video technology will be invited to join the meeting by phone. Makeup sessions will continue to be offered by phone. Treatment session handouts will be sent to participants by email. Since weight will no longer be measured in person at group meetings, all participants will be sent an EatSmart Precision Digital Scale. Prior to group meetings, participants will be asked to email the study coordinator their weight. This will allow the group leader and study team to continue to monitor participant weight loss for clinical purposes.

Outcome assessment visits

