Participants will be expected to attend 4 assessment visits throughout the course of the study: at baseline, week 20, week 46, and week 72 (or within 4 weeks of each assessment period). Three of these assessment visits (baseline, week 20, and week 72) will include a fasting blood test, which will include a comprehensive metabolic panel (CMP), lipid panel, insulin, high sensitivity C-reactive protein (hs-CRP), and hemoglobin A_{1c}. These tests will require approximately 34 mls of blood. Blood pressure, pulse, and waist measurement will also be measured at these outcome assessment visits, and weight will be measured at all assessment visits.

Participants will also be asked to monitor their physical activity and complete questionnaires at baseline, week 20, week 46, and week 72. Questionnaires will be completed online or administered/returned via mail or at scheduled group sessions. Accelerometers will be administered at scheduled group sessions or assessment visits and returned in person or by mail, with an accompanying brief interview to assess activity over the past week (in person or by phone).

Adjustments to outcome assessment visits due to COVID-19. During the pandemic, in-person assessment visits will be replaced with remote assessments whenever possible. Specifically, all week 46 assessment visits will be conducted remotely for the duration of the pandemic. If permitted by the city, institution, and funding sponsor, week 20 and week 72 assessment visits will be offered in-person, in order to allow for the measurement of blood pressure and a fasting blood test. All local and institutional safety regulations will be followed when conducting in-person visits. Participants with safety concerns or other barriers that prevent them from attending in-person assessment visits will be offered remote assessments without penalty.

Remote assessment visits will be scheduled during the morning and will involve a brief phone call with the study coordinator, measurement of weight (and for weeks 20 and 72, measurement of waist circumference), monitoring of activity with an accelerometer device, and completion of online questionnaires. As described above, all participants will be sent an EatSmart Precision Digital Scale (with a tape measure included in the package). For remote assessments, participants will be asked to use the EatSmart scale to weigh themselves in duplicate, in kilograms, in the morning before eating anything. Participants will be asked to send

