Weight bias coping and internalization. Participants will complete the WBIS (described previously) at screening and weeks 20, 46, and 72. In addition to scoring this measure on its continuous scale, the percentage of participants who do and do not meet the eligibility criterion cutoff score (4 or above) will be calculated at weeks 20, 46, and 72, as a measure of "remission" from elevated WBI. Participants will also complete additional measures of stigma, quality of life, stress, and depression at randomization and all subsequent assessment times. Stigma questionnaires will include the Weight Self-Stigma Questionnaire (WSSQ; an alternative measure of WBI),⁷³ Fat Phobia Scale (a measure of stereotype endorsement),⁷⁴ and the Everyday Discrimination Scale (an assessment of unfair treatment in daily life for a variety of reasons, including weight).⁷⁵ The WBIS, WSSQ, Fat Phobia Scale, and Everyday Discrimination Scale are widely used and well validated.^{37,76-81} Additionally, an assessment of weight stigma coping strategies⁸² will be completed to assess the frequency with which participants engage in adaptive and maladaptive behaviors (e.g., exercising more vs. avoiding physical activity) in response to weight stigma. At baseline only, participants will complete the Weight Stigma Timing of Life Questionnaire to assess their history of weight-stigmatizing experiences, and the Adverse Childhood Experience Questionnaire to assess experiences of childhood trauma.⁸³ Participants will also complete the Impact of Weight on Quality of Life Questionnaire-Lite (IWQOL),⁸⁴ which contains five subscales that include items assessing distress due to weight-stigmatizing situations and weight-based discrimination. Participants will complete the Perceived Stress Scale (PSS)⁸⁵ to determine self-reported daily stress, the Questionnaire for Eating and Weight Patterns (QEWP)⁸⁶ to assess disordered eating, and the Patient Health Questionnaire (PHQ-9)⁸⁷ to assess

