symptoms of depression. Participants will complete the Body Appreciation Scale⁸⁸ to assess changes in body positivity. Additionally, participants will complete a brief questionnaire assessing the frequency with which they self-monitor their weight and eating (along with food records which will be collected from participants at all group meetings to assess days of recorded food intake and activity), and treatment acceptability will be assessed at weeks 20 and 72. Participants in the stigma + BWL intervention group are predicted to show greater reductions in all measures of stigma and distress than participants in the BWL group at weeks 20, 46, and 72.

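### Follow-up questionnaires may be administered at treatment group sessions, and only the stigma arm's sessions address the constructs rated: a cheap, low-priority fix for exploratory self-report outcomes

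*Combined protocol and SAP*

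**What the plan says.** Section 6.2 (Outcome assessment visits) has participants "complete questionnaires at baseline, week 20, week 46, and week 72". On how this is done it says: "Questionnaires will be completed online or administered/returned via mail or at scheduled group sessions". No section makes one mode the default, requires the two arms to use the same mode, or says who distributes and collects the forms.

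The sessions differ by arm. For stigma + BWL, Section 6.2 says: "Beginning at week 5, the 60-minute BWL sessions will be followed by 30 minutes devoted to stigma-related content". The maintenance sessions to week 72 return to this material. In the BWL arm the sessions continue "with an additional 30 minutes devoted to discussing recipes and food preparation".

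On timing, Section 6.3 says: "Participants will complete the WBIS (described previously) at screening and weeks 20, 46, and 72". Section 6.1 adds that the screening WBIS and two other instruments "will be mailed or emailed to eligible participants following the phone screen and completed by them prior to their screening/informed consent visit", so the baseline WBIS is answered away from any treatment session.

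Section 6.3 predicts that the stigma arm will show "greater reductions in all measures of stigma and distress than participants in the BWL group at weeks 20, 46, and 72". Section 6.2 intends self-efficacy to rise. Section 7 treats all secondary outcomes as exploratory, says the trial is not powered for psychosocial variables, and tests at a two-sided 0.05 level. During the pandemic, remote assessments use online questionnaires, due by the morning of the assessment.

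**The concern.** The WBIS, the other stigma scales, the Body Appreciation Scale and the exercise self-efficacy scales rate what one arm's sessions work on and the other arm's sessions do not. If a form is filled in at a session, any effect of the setting on the answers (priming, or a wish to give the answer the session favours) differs by arm. It would lower reported WBI and distress and raise reported self-efficacy in the stigma arm, which is the direction of the hypotheses in each case.

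Three features of the plan add to this:

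- The baseline WBIS is completed outside treatment. An in-session follow-up form would change the setting within the same person, so the change score would mix setting with effect.
- WBI remission is defined by the same cutoff of 4 that qualifies people for entry. A small reporting shift can reclassify someone who entered just above it.
- Section 7 may explore attendance in relation to change in WBI. Only attenders can complete a form at a session, so mode would be entangled with attendance, and no record of mode is specified.

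These measures show whether the intervention reached its intended target, and Section 7 says the secondary findings will inform larger studies. A response tied to the setting could not be told apart from a lasting fall in WBI.

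**Working it through.** The plan gives no figure for reporting bias, for the share of forms completed in session, or for the mix of modes. The check therefore sets the passages side by side and then shows how a bias of assumed size would carry through.

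**1. Is the setting arm-dependent?** Section 6.2 permits questionnaires to be administered at group sessions. The same section gives those sessions stigma content in one arm and recipe content in the other. No section separates questionnaire completion from treatment staff. So the permission exists, the content differs on the constructs rated, and no safeguard is written down.

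**2. The plan's own sample size.** This supplies the number of completers; the point does not otherwise depend on it. Inputs from Section 7: difference 4, SD 7, ICC 0.80, 4 assessments, 80% power, two-sided 0.05, 20% attrition.

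- n per arm = 2 × [7 × (1.960 + 0.842) / 4]² × (1 + 3 × 0.80) / 4 = 48.07 × 0.85 = 40.9, rounded up to 41.
- Allowing for attrition: 41 / 0.80 = 51.25, rounded up to 52 per arm, 104 in total. This matches the plan.
- Expected completers: 52 × 0.80 = 41.6 per arm.

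**3. Illustration of size.** Assumptions, none of them from the documents: no true effect; each form completed in session by a stigma-arm participant is shifted by b SD in the favourable direction; BWL-arm forms and out-of-session forms are not shifted; a share s of stigma-arm forms is completed in session; simple two-group comparison at one time point.

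- SE of the standardized difference = √(2 / 41.6) = 0.219.
- Shift in the test statistic: δ = s × b / 0.219.
- Rejection probability = 1 − Φ(1.96 − δ) + Φ(−1.96 − δ).

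For b = 0.2 and s = 1, δ = 0.2 / 0.219 = 0.91, and the rejection probability is 14.9%.

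| Shift per in-session form | All in session | Half | A quarter |
|---|---|---|---|
| 0.2 SD | 14.9% | 7.4% | 5.6% |
| 0.5 SD | 62.6% | 20.7% | 8.8% |

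With all forms in session, shifts of 0.1 and 0.3 SD give 7.4% and 27.7%. If all 52 per arm contribute instead of 41.6, the 0.2 SD all-in-session figure is 17.5%. The nominal rate is 5%. What matters is the average shift over the arm, s × b, so the result falls quickly as the in-session share falls.

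**The case against.** The strongest reply is that the sentence may describe logistics only. It pairs completion with the online route and uses a joint term for giving out and handing back with mail and sessions, which fits a paper packet filled in at home. Section 6.3 lists about 16 instruments, and the 90-minute meeting is fully allocated from week 5 (60 + 30 minutes). If forms are only handed out and collected at sessions, most of the mechanism disappears. This reading is fair, but the wording also covers filling in a form on the spot, and nothing rules that out.

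A reader might also infer that forms are answered in front of the group leader, straight after stigma content, by participants taught to report less. The documents do not support this. They do not say who is present or when in a meeting a form would be filled in. The stigma segment comes last, so a form completed on arrival would precede that day's segment. The sessions aim to reduce WBI itself; reporting bias is plausible but not shown. For self-efficacy the risk runs upward, not downward.

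Other limits also stand. Online and mail are equal options. During the pandemic group sessions are virtual, all week 46 assessments are remote, and remote assessments use online questionnaires. Participants who know their treatment can give favourable answers by any mode, so moving the form removes only part of the bias. Finally, dropping a collection route could cost some self-report data in a trial that already expects 20% attrition.

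**Conclusion.** The point holds as a cheap, low-priority improvement. The plan permits an arm-dependent setting for rating the constructs taught in one arm, and it sets no rule on mode, handling or consistency. That is avoidable.

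The reach is limited to H4, the WBI remission analysis and the self-efficacy part of H2. It would be wrong to infer that the trial's main result is at risk: the primary outcome is percent weight loss, not a questionnaire. Nor is a formal test of mechanism undermined, because Section 7 plans no mediation analysis.

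The size is unknown. The false-rejection figures (about 15%, 7% and 6% for an assumed 0.2 SD shift with all, half or a quarter of forms in session) illustrate sensitivity. They are not estimates of this trial's error rate, because neither the shift nor the in-session share is given.

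**What to change.** In Section 6.2 (Outcome assessment visits), replace the permission with one procedure for both arms:

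- Questionnaires are completed outside group sessions, online by default, with paper as backup. If a session falls on the same day, they are completed before it.
- Sessions may be used only to hand out or return sealed forms, handled by the study coordinator and not by the group leader.
- The mode and date of completion are recorded for every questionnaire.
- Any forms already completed in session are flagged, and Section 7 gains a sensitivity analysis of the affected self-report outcomes that takes them into account.

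The online and mail routes already exist in the protocol, and the remote-assessment procedure already has the coordinator confirm that questionnaires are complete. The cost is a small operating rule, more reminders and possibly slightly lower completion. Keeping sessions as a place to hand out and return sealed forms limits that loss for participants who find online completion difficult.

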6.2 Study Visits

Screening visit. The following procedures will be completed at the screening visit as discussed above: informed consent, medical history, weight, height, and meeting with psychologist whose assessment will be used as a part of determining the subject's eligibility for the study. This medical history will be reviewed by the study physician or nurse practitioner to determine whether there are any contraindications to weight loss. These contraindications include but are not limited to: any major active kidney, liver, cardiovascular, or cerebrovascular disease; type 2 diabetes; or the use of any medications that significantly affect weight (weight loss or weight gain, including steroids). Female participants will be ineligible for the study if they are pregnant or nursing. Applicants with a history of cardiac events or other significant CVD risk factors may also be asked to supply a letter from their primary care physician providing medical clearance for them to participate in this study. Applicants will be required to monitor their food intake following the screening visit and return their food records before being provisionally accepted into the study.

Randomization visit. Within one month of the start of the group intervention, participants will attend a visit in which their weight and blood pressure will be measured and, if they still meet all study criteria, they will be randomized to their treatment group. Accelerometers will be given to participants to monitor their activity for 7-10 days. Participants will return their accelerometers in person, at which time their activity for the past week will be assessed with a structured interview. Participants may be held financially responsible if the accelerometer is lost, stolen, or not returned.

If a participant is randomized but no longer able to attend groups as scheduled, it may be available to them to begin the group intervention, in the same treatment condition as assigned at randomization, in a subsequent cohort. In this case, baseline measurements will be repeated within one month of the start of treatment.

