their weights to the study coordinator; when possible, they will be asked to take pictures of their weight with their phone, and then weigh their phone and send all information/pictures to the coordinator. For weeks 20 and 72 assessments, participants will also be provided with instructions to measure their waist circumference in duplicate with the EatSmart tape measure and will send their measurements to the study coordinator by email. For all remote assessments, accelerometer devices will be delivered to each participant's home, and participants will be asked to begin to wear the device on the morning of their scheduled remote assessment. Participants will also be asked to complete their online questionnaires by the morning of their remote assessment. The study coordinator will have a brief phone call with each participant on the morning of their remote assessment to confirm that the weight/waist measurements have been received, the participant is wearing the accelerometer, and all questionnaires are completed. The coordinator will also conduct a brief assessment by phone of any changes in the participant's health and medications since the last study visit, and the study nurse practitioner will follow up with participants about these changes as needed. Participants who complete either in-person or remote assessments will be able to return their accelerometers by mail using a prepaid shipping label. The study coordinator will schedule an additional phone call to instruct participants when to return the device and to conduct a brief interview assessing their physical activity over the past week.

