6.3 Outcome Measures

Primary outcome. Percent weight loss from baseline to week 72 is the study's primary outcome. At week 72, participants in the stigma + BWL intervention are predicted to maintain their 9% reduction in initial weight, as compared to a significantly smaller 5% reduction in the BWL alone group. Duplicate measures of height (with a wall-mounted stadiometer; Veeder-Root, Elizabethtown, NC) will be obtained at screening, and weight (with a digital scale; Detecto, model 6800A) will be measured at screening, randomization (baseline), and at weeks 20, 46, and 72. Weight will also be measured at all group sessions. Percent weight loss from baseline to weeks 20 and week 46 will be assessed as secondary outcomes, along with categorical weight loss at weeks 72, 46, and 20 (loss of $\geq 5\%$ and $\geq 10\%$ of initial body weight at each time point). Participants in the BWL group are predicted to lose 8% of their initial weight at week 20. Participants in the stigma + BWL group are expected to lose 1% more of their initial weight (9%) at week 20 due to greater engagement in physical activity.

Secondary outcomes.

Physical activity. All participants will be given triaxial accelerometers (ActiGraph GT9X) to wear on their wrist for a 1-week period within 4 weeks of each assessment period (baseline and weeks 20, 46, and 72). Accelerometry has been used in numerous clinical trials,⁶²⁻⁶⁵ and the ActiGraph to be used in this study was adopted in the 5-year extension of the Look AHEAD study. Established activity counts will be used to identify thresholds of physical activity (sedentary, light, moderate, vigorous).⁶⁶ Self-reported physical activity will be assessed with the Paffenbarger Physical Activity Questionnaire⁶⁷ to obtain specific information on the types of activity participants engage in, and a brief questionnaire used in prior studies⁶⁸ to collect data on sedentary behavior. Self-efficacy will be assessed with the Self-Efficacy for Exercise Scale⁶⁹ Exercise Outcome Expectations and Barriers Scale (perceived barrier items only),⁷⁰ and Weight and

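### Pandemic-period week-72 weights may come from a home scale read and sent in by the participant, while baseline comes from the clinic scale, and the analysis plan neither distinguishes nor calibrates the two

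*Combined protocol and SAP*

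**What the plan says.** Section 6.3 defines the endpoint: "Percent weight loss from baseline to week 72 is the study's primary outcome". It names one device for every assessment: "weight (with a digital scale; Detecto, model 6800A) will be measured at screening, randomization (baseline), and at weeks 20, 46, and 72". The baseline weight is taken in person; at the randomization visit in section 6.2, "participants will attend a visit in which their weight and blood pressure will be measured".

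The COVID-19 adjustments in section 6.2 change this for pandemic-period visits. Remote assessment becomes the default where feasible. Week 46 is always remote. Weeks 20 and 72 are offered in person if the city, institution and funder allow it, and "Participants with safety concerns or other barriers that prevent them from attending in-person assessment visits will be offered remote assessments without penalty". At a remote visit, "participants will be asked to use the EatSmart scale to weigh themselves in duplicate, in kilograms, in the morning before eating anything". Participants send the readings to the coordinator, and "when possible, they will be asked to take pictures of their weight with their phone, and then weigh their phone".

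The primary model in section 7 contains treatment group, time (weeks 20, 46, 72) and selected baseline covariates. The optional sensitivity analyses concern events that change true weight. The optional exploratory analyses cover cohort, meeting time, group leader and attendance. Weighing mode appears in none of them.

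**The concern.** A participant weighed by staff on the clinic scale at baseline and at home at week 72 contributes a percent change made of true change plus any difference between scales, settings and recorders. The covariate rule admits only baseline variables, so mode, which arises after randomization, cannot enter through it. The plan pools both kinds of weight without a way to size the difference.

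Week-72 weight carries the sole primary outcome. The same weights feed the responder outcomes and the weight trajectory, and the trajectory matters in a trial about maintaining loss. Because week 46 is entirely remote during the pandemic while weeks 20 and 72 are mixed, an offset would also appear as a change over time.

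**Working it through.** **Inputs from the documents (sections 6.3 and 7).** Expected week-72 losses 9% and 5%; SD 7 points; difference 4 points; 52 per arm; 20% attrition; ICC 0.80; 4 assessments; two-sided alpha 0.05; power 80%.

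**Inputs assumed, because the documents give none.** Remote share at week 72, q = 30-70%; home-scale offset b = 0.5-2 points of percent weight; arm difference in reporting error r = 0.5-1.0 point; extra random error e = 1-3 points. Remote and in-person participants are taken to have the same true mean loss.

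**1. The plan's sample size.** Repeated-measures factor = (1 + 3 × 0.80)/4 = 0.85. n per arm = 2 × (1.960 + 0.842)² × 7² × 0.85 / 4² = 40.9, rounded up to 41. Then 41/0.80 = 51.25, so 52 per arm and 104 in total. The stated figure reproduces. With 52 × 0.80 = 41.6 completers per arm, power is 80.7%. Weighing mode does not alter this arithmetic.

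**2. Within-arm loss.** Shift = b × q. For b = 1 and q = 0.3-0.7, each arm's mean loss moves by 0.3-0.7 points. If everyone were remote, b = 0.5-2 would move it by 0.5-2 points.

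**3. Pattern over time.** With week 46 all remote and share q remote at weeks 20 and 72, the offset at week 46 exceeds that at the other two weeks by b × (1 − q). For b = 1 and q = 0.3-0.7 this is 0.7-0.3 points with no change in true weight. It applies to participants whose visits all fall in the pandemic period.

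**4. Responder rates.** With normal losses, P(loss ≥ t) = 1 − Φ((t − mean − b)/7). For remote weights reading 1 point low (b = 1):

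| Arm | Threshold | No offset | Remote participants, b = 1 |
|---|---|---|---|
| BWL | ≥5% | 50.0% | 55.7% |
| BWL | ≥10% | 23.8% | 28.4% |
| Stigma + BWL | ≥5% | 71.6% | 76.2% |
| Stigma + BWL | ≥10% | 44.3% | 50.0% |

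Arm-wide in BWL at q = 0.3-0.7, the ≥5% rate moves by 5.7 × 0.3 to 5.7 × 0.7 = 1.7-4.0 points, and the ≥10% rate by 4.6 × 0.3 to 4.6 × 0.7 = 1.4-3.2 points. With the opposite sign (b = −1), the ≥5% rate among remote BWL participants falls to 44.3%.

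**5. Arm contrast.**
- Common offset: bias = b × (difference in remote share). Equal shares give 0. A 20-percentage-point difference in share gives 0.5 × 0.2 to 2 × 0.2 = 0.1-0.4 points.
- Reporting error that differs by arm, equal shares: bias = q × r = 0.3 × 0.5 to 0.7 × 1.0 = 0.15-0.7 points, at most 0.7/4 = 17.5% of the planned difference.

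**6. Random error.** With SD = √(7² + e²) and the 0.85 factor kept, e = 1, 2 and 3 points lower power from 80.7% to 79.9%, 77.6% and 73.8%.

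**The case against.** The remote procedure has real safeguards: duplicate readings, one home-scale model for everyone, a morning reading before eating, photographs where obtained, and a same-morning call from the coordinator. The call confirms receipt rather than accuracy. Weighing the phone reads most naturally as a correction for holding it, not as calibration against the clinic scale. Both arms follow the same procedure, so a common offset with equal remote shares cancels in the primary contrast. Responder rates are secondary, and section 7 calls all secondary outcomes exploratory. All of this stands, and it limits the point.

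Several stronger readings do not hold:

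- A reader might infer that participants simply choose how they are weighed. In-person visits depend first on outside permission, and the opt-out is for concerns or barriers that prevent attendance. Preference is only part of it.
- A reader might infer that remote weights are fasting and baseline weights are not. No fasting rule is given for the baseline weighing. Section 6.2 places a fasting blood test at baseline, while section 6.3 places blood samples at screening. Only scale, setting and recorder certainly differ.
- A reader might infer that dependence on remote weights could never be examined. The coordinator receives the readings and photographs, so source records should identify mode. What is missing is a planned variable and a planned analysis.

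The safeguards and the equal procedures do not measure the offset between the two scales, and they do not protect the within-arm results.

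**Conclusion.** The point holds in limited form. For pandemic-period visits, the plan compares a clinic-scale baseline with a week-72 weight that may be read at home and sent in by the participant, and it neither separates nor calibrates the two. The share of visits affected is unknown. The certain exposure is to within-arm losses, responder rates and the pattern over weeks 20, 46 and 72. Its size depends on an offset and a remote share that the documents do not give: under the 1-point, 30-70% illustration, about 2 to 4 points on the BWL ≥5% rate, in either direction according to the sign of the offset.

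A reader might infer that the primary arm contrast is biased, because one arm is treated for weight-related self-stigma and might report or attend differently. That is possible, but no figure in the documents supports it, its direction is unknown, and the bias is zero if offset and remote share are balanced. The 0.15-0.7 point range rests wholly on assumption and stays well below the planned 4 points. This is a worthwhile, inexpensive improvement and not a demonstrated flaw in the primary test.

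**What to change.** 1. Record mode (clinic or remote), scale and photo status for every assessment weight, and report them by arm and week.
2. Ask participants who attend in person at weeks 20 and 72 for a same-morning reading on the EatSmart scale they already have. Estimate the home-minus-clinic offset and report a week-72 analysis with remote weights corrected for it. State that this addresses scale and setting, not misreporting, because these participants know that staff will weigh them.
3. Pre-specify a sensitivity analysis of the week-72 contrast that uses only clinic-measured or photo-verified weights, with the others treated as missing in the same mixed model.
4. Reconcile section 6.3, which names the clinic scale at weeks 20, 46 and 72, with the remote procedure in section 6.2.

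Cost: a few data fields, one extra home reading for in-person attendees, and two further model runs. The verified-only analysis loses precision and may introduce selection, since mode depends partly on barriers and concerns. It should therefore remain a sensitivity analysis and not replace the primary one.
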